2.4.4.1 Analysis of primary effectiveness variable – procedure robotic success

As per section 2.1.3.1 each anastomosis for each patient in the FAS will be assigned to ‘Yes’ or ‘No’ for procedure robotic success. This represents a binary outcome. The analysis of this variable is at the anastomosis level.

For each surgery type (replantation, free flap or lymphatic surgery) stratified frequency tables will be presented stratified by subpopulation (prospective/retrospective) and recipient site/location. The denominator is the number of anastomoses. The proportion of anastomoses classified as a robotic success by stratum and overall for each surgery type will be presented with 95% confidence limits. Results will also be presented on a forest plot.

For replantations a further stratifying variable will be included, namely procedure type (free/nerve).

For each surgery type, a generalized linear mixed model (GLMM) will be used to estimate the percentage of anastomoses classified as robotic success. In SAS, PROC GLIMMIX will be utilized to analyze the data. Subpopulation (prospective/retrospective), recipient site/location and surgeon experience will be included as fixed effects, and surgeon as a random effect. Procedure number (within a surgery type) and anastomosis number (within a procedure) will be included as random terms to acknowledge the dependence in the data (see note above). From the model the adjusted rate of robotic success will be obtained, with 95% confidence limits, for each type of surgery overall and by recipient site/location, by surgeon experience and by subpopulation. (Model 1).

Fixed effects

For free flaps, recipient site will be head and neck, extremities, breast or other.

For lymphatic surgery location will be heads and neck, upper limbs or lower limbs

For replantations there will also be a factor for procedure type (free or nerve), as well as recipient site (as for free flaps) (Model 1a) and results also obtained by procedure type (free/nerve).

For all types of surgery, surgeon experience is classified as microsurgeon, fellow, resident.

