1.7 Determination of sample size

The planned minimum sample size is 402 patients. The primary endpoint for the study is technical performance, assessed as a binary outcome procedural success Yes/No. Procedural success will be assessed at the anastomosis level; each patient may have > 1 anastomosis. Based on data published in the medical literature (see RASM Literature Review Report [5]), the traditional failure and complication rate for vascular anastomoses is 15%, implying a success rate of 85%. The study will have 85% power to conclude that a success rate using Symani of 89% (or higher) is better than the literature value if a minimum of 402 anastomoses operations are performed. The percentage success will be estimated and exact 95% confidence limits calculated. If the lower 95% confidence limit exceeds 85% then the conclusion can be reached that Symani is superior to manual surgical methods. As each patient may have more than one anastomosis operation, the number of anastomoses will be ≥ 402 from 402 patients, providing increased power. As the number of anastomoses/patient is unknown at the time of study design, the conservative approach of recruiting 402 patients has been followed.

The number of patients missing a response for the primary endpoint will be monitored and additional patients may be recruited if deemed necessary.

There will be no predetermined limit to the number of sites that can participate in the study. Patients enrolled under the retrospective data collection protocol addendum will contribute to the planned sample size for the entire study (prospective plus retrospective).

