2.4.4 Analysis of effectiveness variables

Note on analysis models/approach.

For all binary outcomes a simple frequency table presenting number and percentage (with confidence limits) will be produced, where the denominator will be the unit of analysis (patient, surgery type, procedure or anastomosis). The confidence limits produced will be biased as they assume independent observations whilst repeat assessments on the same patient (ie > 1 anastomosis/procedure, >1 procedure/patient) are not independent.

To explore the extent of dependence in the data, a table will be produced to describe the hierarchy in the data (as per fig 1), namely:

- Number of patients.
- Number of surgery types (flap, replantation, lymphatic)/patient (i.e. 1, 2 or 3 different types of surgery).
- Within surgery type, number of procedures/patient (i.e. number of flaps, number of replantations, number of lymphatic procedures).
- Within each procedure, number of anastomoses/procedure and also number of anastomoses/patient.

In the simplest scenario there will be one surgery type/patient, one procedure/patient and for that procedure only one anastomosis (so at all levels there is one/patient).

The most complex structure is each patient has all three surgery types, with multiple procedures of each type and for each procedure there are multiple anastomoses.

In addition to these levels of dependence due to repeated observations on the same patient, the results are expected to be influenced by surgeon. Accordingly, for the main analysis of all effectiveness endpoints, a mixed model will be employed where surgeon will be included as a random term.

All models will be fitted separately for each surgery type (free flaps, replantations, lymphatic).

In all models fixed effects for subpopulation (prospective/retrospective) and recipient site/location will also be included to facilitate estimation by subpopulation and recipient site/location. For analysis of replantations a further fixed effect will be included for procedure type (free or nerve).

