2.4.4.3.1 Free-flap survival rate at 30 days

As per section 2.1.3.5.1 each flap for each patient in the FAS will be assigned to 'Yes' or 'No' for free flap survival at 30 days. This represents a binary outcome. The analysis of this variable is at the procedure (flap) level. Summary and analysis will be as described above for flap loss/failure (Model 4).

Sponsor: MMI Product: Symani system for microsurgical anastomosis Study: PRIMO	
Statistical Analysis Plan Final 22 November 2024	

In addition, the effectiveness of the Symani System will be evaluated for consistency with the free flap success rates reported in the UK National Flap Registry [1], where the overall free flap survival rate was 96.0% (95% confidence limits, 95.4%, 96.6%)."

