Appendix 1. Summary of endpoints, unit of analysis and analysis method

Endpoint	Level	analysis
Robotic success	Anastomosis	GLMM. Bernoulli form by stype Fixed: recipient site/location, subpop For replantations also include procedure type (free or nerve) Random surgeon, procedure number anastomosis number, subject=patient. Model 1/1a.
Robotic usability	Patient	GLMM Binomial form as nsuccess/npats by stype Fixed: recipient site/location. For replantations also include procedure type (free or nerve) Random surgeon. Model 2./2a
Anastomosis time	Anastomosis	GLMM normal by stype Fixed: recipient site/location, subpop For replantations also include procedure type (free or nerve) Random surgeon, procedure number anastomosis number, subject=patient. Model 3/3a
Intra-operative redo	Anastomosis	Model 1/1a
Post-op redo	Procedure	GLMM Bernoulli form by stype Fixed: recipient site/location, subpop For replantations also include procedure type (free or nerve),

Sponsor: MMI Product: Symani system for microsurgical anastomosis Study: PRIMO	
Statistical Analysis Plan Final 22 November 2024	

		Random surgeon, procedure number subject=patient. Model 4/4a
Complications	Patient	Safety endpoint. Summaries of AEs
Warm ischemia time		
Flap loss/failure	Procedure	Model 4/4a
Limb volume reduction	Procedure	GLMM normal Fixed timepoint. Cov baseline vol. Random surgeon, procedure number subject=patient. Model 5.
Free flap viability at 30 days	Procedure	Model 4/4a
Intra-operative anastomosis patency	Anastomosis	Model 1/1a
Rate of intra-operative approach change	Anastomosis	Model 1/1a
Freedom from device related SAE at discharge	Patient	Simple frequency and exact CL
Freedom from device related AE at discharge	Patient	Simple frequency and exact CL
All cause re-admission rate	Patient	KM. Use PL to get rate within 30 days
All cause re-op rate	Patient	KM. Use PL to get rate within 30 days
All cause mortality rate	Patient	KM. Use PL to get rate within 30 days
Length of hospital stay	Patient	Descriptive stats

PRIMO Statistical Analysis Plan

Final Audit Report

2024-12-13

Created:	2024-12-11
By:	[name] ([contact])
Status:	Signed
Transaction ID:	CBJCHBCAABAAHjF3YtYJkG7xb1_tZngZ89-skKZM8HiF

"PRIMO Statistical Analysis Plan" History

-  Document created by [name] ([contact])
2024-12-11 - 4:57:01 PM GMT
-  Document emailed to [name] ([contact]) for signature
2024-12-11 - 4:57:09 PM GMT
-  Document emailed to [name] ([contact]) for signature

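### The main-analysis mixed model is said to estimate the percentage of anastomoses that succeed, but with no averaging over its random effects its usual output is a different rate, expected to lie further from 50%

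*SAP*

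**What the plan says.** SAP 2.4.4.1 sets the target of the primary model: "a generalized linear mixed model (GLMM) will be used to estimate the percentage of anastomoses classified as robotic success". The tool is PROC GLIMMIX, and the output is described as follows: "From the model the adjusted rate of robotic success will be obtained, with 95% confidence limits, for each type of surgery overall", with further rates by site, surgeon experience and subpopulation. Appendix 1 gives the random part as "Random surgeon, procedure number anastomosis number, subject=patient. Model 1/1a".

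On the model's standing, SAP 2.4.4 says that "for the main analysis of all effectiveness endpoints, a mixed model will be employed where surgeon will be included as a random term". The same section expects results to depend on the surgeon and warns that the simple confidence limits are biased because they assume independence. Models are fitted separately for each surgery type. Procedure and anastomosis terms enter as required, once the table describing the hierarchy has been seen. SAP 2.5.6 gives a default variance-components structure but no variance.

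There are two external rates. SAP 1.7 derives 85% from the literature, announces the observed percentage with exact 95% limits, and then states: "If the lower 95% confidence limit exceeds 85% then the conclusion can be reached that Symani is superior to manual surgical methods". SAP 2.4.4.3.1 analyses 30-day flap survival with frequency tables and Model 4, then calls for an evaluation of consistency with a registry figure of 96.0%. It does not say which estimate is compared.

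The SAP does not state the link, the estimation method, the back-transformation, any averaging over random effects, or the weights given to site, experience and subpopulation.

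**The concern.** The percentage of anastomoses that succeed is a population average over all surgeons and patients. A logistic model with random effects is built on the logit scale. When its linear predictor is back-transformed with the random effects at zero, the result is the rate for a surgeon and patient at the middle of the random-effect distribution. The inverse logit is curved, so the two rates differ whenever the random-effect variance is positive, and the gap grows with that variance.

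If the plan is followed with standard software output, the main-analysis rate is therefore not the quantity that 2.4.4.1 names. The expected direction favours the device for good and bad outcomes alike, and more variation between surgeons widens the gap.

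Model 1 has a further problem. Anastomosis number within procedure has one 0/1 result per level. Bernoulli data carry essentially no information on that variance, yet any positive estimate enters the back-transformation.

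**Working it through.** **Inputs.** From the documents: 85% benchmark, 89% alternative, 85% power and 402 anastomoses (SAP 1.7); 96.0% (SAP 2.4.4.3.1); random surgeon, procedure and anastomosis terms (Appendix 1). Assumed: logit link, one normal random intercept with logit-scale SD *s*, and an adjusted rate equal to the inverse link at random effects zero. The documents give no *s*, so a range is shown.

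**The plan's own figure.** SAP 1.7 states a power but no conditional or marginal rate. Under its exact two-sided rule, success needs at least 356 of 402 (88.6% observed; lower limit 85.03%). The one-sided error at a true 85% is 2.4%, and the power at 89% is 64.9%, so the stated 85% is not reproduced. That is a separate matter. Its relevance here is that the exact rule acts on the observed count and needs no mixed model.

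**Conditional against population rate.** With intercept η:

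- rate at random effects zero = expit(η)
- population rate = ∫ expit(η + s·u) φ(u) du

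Solving the second for η (101-point Gauss–Hermite quadrature) and reading off the first gives:

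| SD *s* | true 85% reads | true 96.0% reads |
|---|---|---|
| 0.25 | 85.3% | 96.1% |
| 0.5 | 86.1% | 96.4% |
| 0.75 | 87.2% | 96.9% |
| 1.0 | 88.6% | 97.4% |
| 1.5 | 91.5% | 98.4% |

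Hand check at *s* = 1: η = 2.048, so expit(η) = 88.6%. Put half the surgeons one SD above and half one SD below: expit(3.048) = 95.5% and expit(1.048) = 74.0%, with mean 84.75%, close to the 85% from full integration.

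For adverse outcomes the picture is mirrored. At *s* = 1 a true redo rate of 15% reads 100 − 88.6 = 11.4%, and a true flap loss of 4.0% reads 100 − 97.4 = 2.6%.

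**Effect of the fitting method.** The surgeon-intercept model was simulated with 20 surgeons × 20, 20 × 7 and 40 × 10 anastomoses, 150 runs each and no covariates. It was fitted by quadrature maximum likelihood and by a pseudo-likelihood method standing in for a GLIMMIX-type fit. For a true 85%:

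| SD *s* | maximum likelihood | pseudo-likelihood | pseudo-likelihood lower limit above 85% |
|---|---|---|---|
| 0.5 | 85.7–85.9% | 85.1–85.2% | 0–3% of runs |
| 1.0 | 87.6–88.4% | 85.8–86.8% | 5–9% |
| 1.5 | 90.2–91.4% | 87.1–89.2% | 10–21% |

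The last column compares with a nominal 2.5% and carries a Monte Carlo error of about 1 to 3 points. Integrating the maximum-likelihood fit over its random effects recovered the crude percentage to within 0.2 points in every setting.

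The direction is not guaranteed. At a true 96% with 20 surgeons × 7 and *s* = 1.5, pseudo-likelihood gave 94.2%.

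**Which comparison uses which rate.** SAP 1.7 pairs 85% with the observed percentage and exact limits. SAP 2.4.4 calls such independence-based limits biased and makes the mixed model the main analysis, and 2.4.4.1 mentions neither exact limits nor 85%. These sections are not reconciled. SAP 2.4.4.3.1 produces both a crude rate and a Model 4 rate and does not choose between them.

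**The case against.** The strongest objection is that the SAP never sets the model's rate against 85%. SAP 1.7 uses the observed percentage with exact limits, which this effect does not touch, and models fitted by surgery type give no single overall rate. Crude proportions are tabulated beside the model, so a divergence would be visible. The 96.0% comparison is only for consistency and has no stated criterion. Redo, flap loss at discharge and usability have no external rate. All of this stands. A reader might infer that the adjusted rates are certain to be too high against 85% and 96.0%, or that the superiority conclusion has an inflated error rate. The documents do not support either reading.

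Other objections also have force. Pseudo-likelihood roughly halves the shift at SD 1.0 or removes more of it, and equal weighting of covariate levels could move an adjusted rate either way. The simulation omits the planned fixed effects. A surgeon-clustered population-average interval was itself above nominal in simulation (4–5% at SD 1.0, 5–8% at SD 1.5), so not all of the excess comes from the choice of rate. The anastomosis term enters only as required, and its added effect was not simulated.

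What remains is that the model declared to be the main analysis does not, with its usual output, estimate the percentage named for it. A crude figure alongside does not cure this, because the SAP itself calls the crude limits biased.

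**Conclusion.** The point holds in this form. SAP 2.4.4.1 names a population percentage, SAP 2.4.4 makes a random-effects model the main analysis, and no step averages over the random effects. The adjusted rate is then expected to lie further from 50% than the named percentage whenever the variance is positive, and the SAP itself expects a surgeon effect.

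The size rests on an assumed SD: about 1 point at SD 0.5, 3.6 points at SD 1.0 and 6.5 points at SD 1.5 for a true 85% in theory, and roughly 0, 1–2 and 2–4 points under pseudo-likelihood. It also rests on a logit link and an inverse-linked least-squares mean, which the SAP does not state. The direction is an expectation, not a certainty.

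The effect reaches the 85% rule only if the model's limit is used in place of the exact limit, and the 96.0% comparison only if the Model 4 rate is the one compared. The change should be made; the point does not show that the planned superiority rule is wrong.

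**What to change.** - In 2.4.4.1, and for Models 1, 2 and 4, state the link and define the reported percentage and its 95% limits as population-averaged. Either integrate the predicted probability over the estimated random effects at the observed mix of the model's covariates, with delta-method or cluster-bootstrap limits, or fit a marginal logistic model (GEE) clustered on surgeon with small-sample-corrected robust limits.
- Drop the anastomosis-number term from the Bernoulli models and use a patient-level intercept.
- State in 1.7 and 2.4.4.3.1 that the population-averaged estimate is the one set against 85% and 96.0%, which also reconciles 1.7 with 2.4.4.
- Keep the conditional mixed model for describing differences between surgeons.

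The cost is SAP wording and a few lines of SAS code; no new data are needed. The reported rates may be slightly less favourable, and the limits need the small-cluster correction when few surgeons contribute.

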2.4.4.2 Analyses of secondary efficacy variables

2.4.4.2.1 Surgeon assessment of robotic usability.

This endpoint is derived from one question on the surgeons usability questionnaire, as defined in section 2.1.3.2.1. This analysis is at the patient level. Frequency tables will be used to present the number of patients where the surgeon classified the procedure as ‘success’, with 95% confidence limits. Results will be presented overall and by surgery type.

Note, this endpoint is for the prospective subpopulation only.

Sponsor: MMI Product: Symani system for microsurgical anastomosis Study: PRIMO	
Statistical Analysis Plan Final 22 November 2024	

The data will be collapsed to surgeon level. For each surgeon the number of patients will be counted (N), as will the number of patients that were classified by the surgeon as 'success'. A generalized linear mixed model (GLMM) will be used to estimate the percentage of patients classified by surgeons as successful. In SAS, PROC GLIMMIX will be utilized to analyze the data. Surgery type (see note below) will be included as a fixed term and surgeon will be included as a random effect.

Surgery type will be included as a fixed term. For patients who had more than one type of surgery, they will be classified as surgery type = 'multiple'.

From the model the overall success rate and success rate by surgery type will be obtained with 95% confidence limits. Model 2.

In addition, results by surgeon (with confidence limits) will be obtained and presented on a forest plot.

2.4.4.2.2 Anastomosis execution time

Robotic usage time, manual suture time and total suture time are derived as described in section 2.1.3.2.2. This analysis is at the anastomosis level.

For each surgery type, results for each variable will be summarized using descriptive statistics overall and by subpopulation (prospective/retrospective) and by recipient site. The denominator for all calculations will be the number of anastomoses.

For each surgery type, a general linear mixed model (GLMM, using SAS proc mixed) will be fitted with time as the outcome and recipient site/location and subpopulation as fixed effects. Procedure number (within a surgery type) and anastomosis number (within a procedure) will be included as random terms to acknowledge the dependence in the data (see note above). For each type of surgery, from the model the adjusted mean time will be obtained, with 95% confidence limits, overall and by recipient site and subpopulation. Model 3.

For replantations an additional fixed effect for procedure type (free or nerve) will be included and results obtained by procedure type (free/nerve). Model 3a.

Separate models will be fitted for robotic time, manual time and total time for each surgery type.

2.4.4.2.3 Intra-operative need to redo the anastomosis.

As per section 2.1.3.2.3 each anastomosis for each patient in the FAS will be assigned to 'Yes' or 'No' for intra-operative redo. This represents a binary outcome. The analysis of this variable is at the anastomosis level.

Summary and analysis will be as described for the primary effectiveness endpoint (model 1/1a).

Sponsor: MMI Product: Symani system for microsurgical anastomosis Study: PRIMO	
Statistical Analysis Plan Final 22 November 2024	

2.4.4.2.4 Post-operative need to redo within 7 days.

As per section 2.1.3.2.4 each patient in the FAS will be assigned to 'Yes' or 'No' for post-operative redo within 7 days for each surgery type. This represents a binary outcome. The analysis of this variable is at the procedure level.

For each surgery type (replantation, free flap or lymphatic surgery) stratified frequency tables will be presented stratified by subpopulation (prospective/retrospective) and recipient site/location. For replantations an additional stratum, procedure type (free or nerve) will be included. The denominator is the number of procedures. The proportion of procedures needing a post-operative redo by stratum and overall for each surgery type will be presented with 95% confidence limits. Results will also be presented on a forest plot

For each surgery type a generalized linear mixed model (GLMM) will be used to estimate the percentage of procedures needing a post-operative redo within 7 days. In SAS, PROC GLIMMIX will be utilized to analyze the data. Recipient site/location and subpopulation (prospective/retrospective) will be included as fixed effects, and surgeon as a random effect. Procedure number (within a patient) will be included as a random term to acknowledge the dependence in the data (namely that each patient may have > 1 procedure and any number may require post-operative redo). From the model the adjusted rate of post-operative redo can be obtained, with 95% confidence limits, for all procedures combined and by procedure type and subpopulation. Model 4.

For replantations, an additional fixed effect of procedure type (free nerve) will be included and results obtained by type. (Model 4a).

If most patients have only one procedure for a given surgery type, then the model will be simplified and the random term for procedure number will be dropped.

2.4.4.2.5 Warm ischemia time (flap and replantations only).

Warm procedure time (see section 2.1.3.3.1 for derivation) will be summarized and analyzed as described for anastomosis time.

